8.4 Dose modification and management of toxicities

All toxicities will be graded according to CTCAE version 4.0. Following the first dose of durvalumab and tremelimumab, subsequent administration of durvalumab and tremelimumab can be modified based on toxicities observed as described in [Sections 8.5, 8.6, and 8.7](#). For adverse events (AEs) that are considered at least partly due to administration of durvalumab or tremelimumab, the following general guidance may be applied:

- Treat each of the toxicities with maximum supportive care (including holding the study therapy suspected of causing the toxicity where required).
- All dose modifications should be documented with clear reasoning and documentation of the approach taken.
- In addition to the criteria for permanent discontinuation of study therapy based on toxicity grade, permanently discontinue study therapy for the conditions outlined in [Section 8.2.2](#).

Table 7. Treatment management for study therapy (durvalumab and tremelimumab)

CTCAE v4.0 Adverse Event	CTCAE v4.0 Grade	Action to be Taken with Study Therapy	
		Tremelimumab	Durvalumab
Cardiac Disorders			
Myocarditis (See Sections 8.5.1 and 8.5.12)	1	For suspected myocarditis: Hold study therapy until full diagnostic work up. Initiate steroid therapy and appropriate management. If study therapy is held, resume after complete resolution to Grade 0 after completion of the steroid taper, resume at the next scheduled dose.	
	2	Hold study therapy dose until resolution to Grade 0. If toxicity rapidly improves to Grade 0, then: The decision to reinstitute study therapy will be based upon treating physician’s clinical judgment and after completion of steroid taper. If toxicity does not rapidly improve, permanently: Discontinue study therapy.	
	3-4	Discontinue study therapy	
Endocrine disorders			
Endocrinopathy (e.g., hyperthyroidism, hypothyroidism, Type 1 diabetes mellitus, hypophysitis, hypopituitarism, and adrenal insufficiency; exocrine event of amylase/lipase increased also included in this section) (See Sections 8.5.1 and 8.5.8).	1	No dose modifications.	
	2	For all patients with abnormal endocrine work up, except those with isolated hypothyroidism or Type 1 DM , and as guided by an endocrinologist, consider short term corticosteroids and prompt initiation of treatment with relevant hormone replacement (e.g., hydrocortisone, sex hormones). Hold study therapy dose until patient is clinically stable. 
 – If systemic steroid therapy has been initiated – after completion of the steroid taper, resume. – If steroid taper completion is > 28 days: discontinue further study therapy. Patients with endocrinopathies who may require prolonged or continued steroid replacement (e.g., adrenal insufficiency) can be retreated with study therapy on the following conditions: 
 – The event stabilizes and is controlled. – The patient is clinically stable as per investigator or treating physician’s clinical judgement. – Doses of prednisone are ≤10 mg/day or equivalent. 	

Table 7 continued on next page.

Table 7. Treatment management for study therapy (continued)

CTCAE v4.0 Adverse Event	CTCAE v4.0 Grade	Action to be Taken with Study Therapy	
		Tremelimumab	Durvalumab
Endocrine disorders (continued)			
Endocrinopathy (e.g., hyperthyroidism, hypothyroidism, Type 1 diabetes mellitus, hypophysitis, hypopituitarism, and adrenal insufficiency; exocrine event of amylase/lipase increased also included in this section) (See Sections 8.5.1 and 8.5.8).	3-4	
For all patients with abnormal endocrine work up, except those with isolated hypothyroidism or Type 1 DM, and as guided by an endocrinologist, consider short term corticosteroids and prompt initiation of treatment with relevant hormone replacement (e.g., hydrocortisone, sex hormones).
 
Hold study therapy dose until patient is clinically stable.
 
 – If systemic steroid therapy has been initiated – after completion of the steroid taper, resume study therapy. – If steroid taper completion is > 28 days: discontinue further study therapy. 
Patients with endocrinopathies who may require prolonged or continued steroid replacement (e.g., adrenal insufficiency) can be retreated with study therapy on the following conditions:
 
 – The event stabilizes and is controlled. – The patient is clinically stable as per investigator or treating physician’s clinical judgement. 
Doses of prednisone are ≤10 mg/day or equivalent.
	
Gastrointestinal disorders			
Diarrhea/Enterocolitis (See Sections 8.5.1 and 8.5.4 .)	1	Maintain study dose schedule without delay; adjust antidiarrheal medication.	
	2	Hold study therapy and adjust antidiarrheal medication. Once event is stabilized to ≤ Grade 1 after completion of the steroid taper, then resume: ↓ one dose level. If steroid taper completion is > 28 days: Discontinue further study therapy.	
	3	Hold study therapy and adjust antidiarrheal medication. If event is stabilized to ≤ Grade 1 within 14 days, after completion of the steroid taper, resume: ↓ one dose level. If there is no improvement within 14 days or steroid taper completion is > 28 days: Discontinue further study therapy.	
	4	Discontinue study therapy	
Hepatobiliary Disorders			
Hepatitis/hepatotoxicity (See Sections 8.5.5 , 8.6.2 , and 8.7 .)	3, 4	Discontinue study therapy	

Table 7 continued on next page.

Table 7. Treatment management for study therapy (continued)

CTCAE v4.0 Adverse Event	CTCAE v4.0 Grade	Action to be Taken with Study Therapy	
		Tremelimumab	Durvalumab
Immune System Disorders			
Allergic reaction/ Infusion reaction (See Table 4 and Sections 8.5.1 and 8.5.2 .)	1	The infusion rate of study therapy may be decreased by 50% or temporarily interrupted until resolution of the event. Maintain study dose level.	
	2	The infusion rate of study therapy may be decreased 50% or temporarily interrupted until resolution of the event. Subsequent infusions may be given at 50% of the initial infusion rate. Once event is stabilized to ≤ Grade 1, after completion of the steroid taper, resume: ↓ one dose level. If steroid taper completion is > 28 days: Discontinue further study therapy.	
	3,4	Discontinue study therapy	
Investigations			
Immune-mediated hepatitis as indicated by: 
 • Alanine transferase (ALT) increased • Alkaline phosphatase increased • Aspartate aminotransferase (AST) increased • Blood bilirubin increased Note: Permanently discontinue study therapy for any case meeting Hy's Law criteria. (See Sections 8.5.5 , 8.6.2 , and 8.7 [Hy's Law].)	1	Monitor LFTs; Maintain study dose level.	
	2	Note: For patients with metastatic liver disease who enter the study with Grade 2 transaminases: Maintain dose and continue study therapy without holding. Otherwise: Hold study therapy. Once elevations have resolved to ≤ Grade 1 and, 
 • No systemic steroid therapy has been initiated then resume: Maintain dose level • Systemic steroid therapy has been initiated – after completion of the steroid taper, resume: ↓ one dose level or discontinue. • If steroid taper completion is > 28 days: Discontinue further study therapy. 	

Table 7 continued on next page.

Table 7. Treatment management for study therapy (continued)

CTCAE v4.0 Adverse Event	CTCAE v4.0 Grade	Action to be Taken with Study Therapy	
		Tremelimumab	Durvalumab
Investigations (continued)			
Immune-mediated hepatitis as indicated by: 
 • Alanine transferase (ALT) increased • Alkaline phosphatase increased • Aspartate aminotransferase (AST) increased • Blood bilirubin increased Note: Permanently discontinue study therapy for any case meeting Hy's Law criteria. (See Sections 8.5.5, 8.6.2, and 8.7 [Hy's Law].)	3	Elevations in transaminases $\leq 8 \times$ ULN and bilirubin $\leq 5 \times$ ULN: Hold study therapy; if elevations resolve to \leq Grade 1 or base line within 14 days , and if 
 • no systemic steroid therapy has been initiated: then resume: Maintain dose or \downarrow one dose level. • systemic steroid therapy has been initiated – after completion of the steroid taper, resume: \downarrow one dose level or discontinue. • If steroid taper completion is > 28 days: discontinue. Note: If elevations do not downgrade to \leq Grade 1 within 14 days OR for elevations in transaminases $> 8 \times$ ULN or bilirubin $> 5 \times$ ULN: Discontinue further study therapy. Discontinue study therapy for any case meeting Hy's law criteria and in the absence of any alternative cause. 	
	4	Discontinue study therapy	
Creatinine increased (Nephritis) (See Sections 8.5.1 and 8.5.6.)	1	Maintain study dose level	
	2	Hold study therapy until resolved to \leq Grade 1 after completion of the steroid taper, resume: \downarrow one dose level. If steroid taper completion is > 28 days: Discontinue further study therapy.	
	3, 4	Discontinue study therapy	
Platelet count decreased (See Section 8.5.11.)	2	Hold until \leq Grade 1 or baseline, then resume and: Maintain dose or \downarrow one dose level.	Hold until \leq Grade 1 or baseline, then resume and: Maintain dose
	3	Hold until \leq Grade 1 or baseline, then resume and: \downarrow one dose level.	Hold until \leq Grade 1 or baseline, then resume and: Maintain dose
	4	Discontinue study therapy	
	Musculoskeletal and connective tissue disorders		
Myositis/Polymyositis (See section 8.5.13)	1	No dose modifications.	
	2	Hold study therapy dose until resolution to Grade ≤ 1 . Discontinue study therapy if it does not resolve to Grade ≤ 1 within 28 days or if there are signs of respiratory insufficiency.	
	3	Hold study therapy dose until resolution to Grade ≤ 1 . Discontinue study therapy if Grade 3 imAE does not resolve to Grade ≤ 1 within 28 days or if there are signs of respiratory insufficiency.	
	4	Discontinue study therapy	

Table 7 continued on next page.

Table 7. Treatment management for study therapy (continued)

CTCAE v4.0 Adverse Event	CTCAE v4.0 Grade	Action to be Taken with Study Therapy	
		Tremelimumab	Durvalumab
Nervous system disorders			
Neurotoxicity (to include but not be limited to limbic encephalitis and autonomic neuropathy, excluding Myasthenia Gravis and Guillain-Barre) (See Sections 8.5.1 and 8.5.9.)	1	Hold study therapy during neurotoxicity work-up. If diagnosis of Myasthenia Gravis or Guillain-Barre is confirmed, discontinue study therapy. Otherwise, maintain study dose level.	
	2,3	Hold study therapy during neurotoxicity work-up. Once elevations have resolved to \leq Grade 1, and if 
 no systemic steroid therapy has been initiated, then resume: \downarrow 1 dose level. systemic steroid therapy has been initiated –after completion of the steroid taper: resume \downarrow 1 dose level or discontinue If steroid taper completion is $>$ 28 days: discontinue further study therapy. 	
	4	Discontinue study therapy	
Peripheral neuromotor syndrome (such as Guillain-Barre and myasthenia gravis) (See Sections 8.5.1 and 8.5.10.)	1	No dose modifications.	
	2	Hold study therapy dose until resolution to Grade \leq 1. Permanently discontinue study therapy if it does not resolve to Grade \leq 1 within 28 days or if there are signs of respiratory insufficiency or autonomic instability.	
	3	Hold study therapy dose until resolution to Grade \leq 1. Permanently discontinue study therapy if it does not resolve to Grade \leq 1 within 28 days or if there are signs of respiratory insufficiency or autonomic instability.	
	4	Discontinue study therapy	
Respiratory, thoracic, and mediastinal disorders			
Pneumonitis/pulmonary infiltrates/other pulmonary events 
 Dyspnea Hypoxia Pneumonitis ILD Pulmonary fibrosis (See Sections 8.5.1 , 8.5.3 , and 8.6.1.)	Hold study treatment until pneumonitis is evaluated.		
	1	Maintain study therapy schedule without delay.	
	2	Hold study therapy. At physician's discretion, once event is stabilized to \leq Grade 1 after completion of the steroid taper, then resume: \downarrow one dose level. If steroid taper completion is $>$ 28 days: discontinue further study therapy.	
3,4	Discontinue study therapy		

Table 7 continued on next page.

Table 7. Treatment management for study therapy (continued)

CTCAE v4.0 Adverse Event	CTCAE v4.0 Grade	Action to be Taken with Study Therapy	
		Tremelimumab	Durvalumab
Skin and subcutaneous tissue disorders			
Rash/dermatitis (e.g., acneiform, maculo-papular) (See Sections 8.5.1 and 8.5.7.)	1	Maintain dose level	
	2	Hold study therapy until resolution to ≤ Grade 1 or baseline and if 
 no systemic steroid therapy has been initiated—resume: Maintain dose level or ↓ one dose level. systemic steroid therapy has been initiated –after completion of the steroid taper: Maintain dose level or ↓ one dose level. If steroid taper completion is > 28 days: discontinue further study therapy .	
	3	Hold study therapy until resolution to ≤ Grade 1 or baseline and if 
 no systemic steroid therapy has been initiated—resume: ↓ one dose level or discontinue. systemic steroid therapy has been initiated –after completion of the steroid taper: ↓ one dose level or discontinue. If steroid taper completion is > 28 days: Discontinue further study therapy .	
	4	Discontinue study therapy	
Rash (e.g., bullous skin formations) (See Section 8.5.7)	All Grades	Discontinue study therapy	
AEs of Non-Immune Mediated Reactions			
AEs of non-immune mediated reaction requiring dose modification per investigator (e.g., Section 8.5.1)	1	Maintain dose	
	2	Hold study therapy until resolution to ≤ Grade 1 or baseline then resume: Maintain dose or ↓ one dose level .	
	3	Hold study therapy until resolution to ≤ Grade 1 or baseline, then resume: ↓ one dose level or discontinue at physician's discretion .	
	4	Discontinue study therapy	

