8.2 Treatment management for durvalumab and tremelimumab

The study treatment schedule should be maintained. If necessary, the timing of a treatment may be adjusted to 3 days earlier or 3 days later than the scheduled date of treatment. All doses administered or missed must be recorded.

8.2.1 *Treatment decisions when therapy must be held*

- In the event systemic steroid therapy is initiated for toxicity management, study therapy must be held. The steroid taper should be completed within 28 days. Study therapy may then be resumed after completion of the steroid taper on Day 1 of the next scheduled cycle.
- Note: Should the steroid taper require a slower rate for completion (i.e., > 28 days), further study therapy doses must be discontinued.
- See [Table 7](#) for treatment management.

8.2.2 *Treatment decisions when therapy must be discontinued*

Treatment must be discontinued if:

- If either durvalumab or tremelimumab must be held for > 28 days of continuous delay for other than steroid taper (e.g., toxicity).
- Consent is withdrawn or patient is lost to follow-up. If consent is withdrawn, the patient will not receive any further investigational product or further study observation.
- An adverse event occurs that, in the opinion of the investigator or sponsor, contradicts further dosing.
- The patient becomes pregnant or intends to conceive a child while actively on study.
- Grade 3 or greater infusion reaction occurs.
- Bullous rash.
- Diagnosis of Guillain-Barre and/or Myasthenia Gravis.
- Initiation of alternate cancer therapy including another investigational agent.
- If tumor progression occurs during study therapy, durvalumab must be discontinued. See [Section 11.0](#).

See [Table 7](#) for additional treatment management requirements. Patients who prematurely discontinue study therapy should complete assessments on [Table 2](#).

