8.3 Dose modifications for durvalumab and tremelimumab

The instructions for management of toxicities during durvalumab and tremelimumab are outlined in [Table 7](#). Dosing of study therapy will be done in tandem:

- When study therapy doses are to be maintained, **both** durvalumab and tremelimumab doses will be maintained on the same dose level.

- When a dose reduction is indicated, **both** durvalumab and tremelimumab will be reduced to the same dose level (e.g., Dose level 1).
- When discontinuation of study therapy is indicated, durvalumab and tremelimumab will be discontinued at the same time.

Table 5. Dose levels for durvalumab

Durvalumab	Dose Level 0 Starting Dose	Dose Level –1	Dose Level –2
		1500 mg	750 mg

Table 6. Dose levels for tremelimumab

Tremelimumab	Dose Level 0 Starting Dose	Dose Level –1	Dose Level –2
		75 mg	40 mg

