- *Grade 2: (including those with symptomatic endocrinopathy)*

For Grade 2 endocrinopathy other than hypothyroidism and Type 1 diabetes mellitus, hold study therapy dose until patient is clinically stable. If toxicity worsens, then treat as Grade 3 or Grade 4. Study therapy can be resumed once event stabilizes and after completion of steroid taper. [See Table 7](#).

 - Consult endocrinologist to guide evaluation of endocrine function and, as indicated by suspected endocrinopathy and as clinically indicated, consider pituitary scan.

- For all patients with abnormal endocrine work up, except those with isolated hypothyroidism or Type 1 DM, and as guided by an endocrinologist, consider short-term corticosteroids (e.g., 1 to 2 mg/kg/day methylprednisolone PO or IV equivalent) and prompt initiation of treatment with relevant hormone replacement (e.g., hydrocortisone, sex hormones).
 - *Isolated hypothyroidism* may be treated with replacement therapy without treatment interruption and without corticosteroids.
 - *Patients with T1DM* may be treated with appropriate diabetic therapy, without study therapy interruption, and without corticosteroids.
 - Once improving, gradually taper steroids (28 days of taper) and consider prophylactic antibiotics, antifungals and anti PJP treatment (refer to current NCCN guidelines for treatment of cancer-related infections [Category 2B recommendation]).
 - For patients with normal endocrine work up (lab or MRI scans), repeat labs/MRI as clinically indicated.
 - Report event to DSSM.
- *Grade 3 or 4:*
For Grade 3 or 4 endocrinopathy other than hypothyroidism and Type 1 diabetes mellitus, hold study therapy dose until endocrinopathy symptom(s) are controlled. Study therapy can be resumed once event stabilizes and after completion of steroid taper.
Patients with endocrinopathies who may require prolonged or continued steroid replacement (e.g., adrenal insufficiency) can be retreated with study therapy on the following conditions: a) the event stabilizes and is controlled; b) the patient is clinically stable as per investigator or treating physician’s clinical judgement; c) doses of prednisone are ≤ 10 mg/day or equivalent.
 - Consult Endocrinology to guide evaluation of endocrine function and, as indicated by suspected endocrinopathy and as clinically indicated, consider pituitary scan.
 - Hospitalization recommended.

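### Pancreatitis alone among the 12 bulleted AESIs has no Table 7 row or 8.5 subsection, so redosing is allowed after a Grade 4 immune-mediated case that settles with a taper of 28 days or less

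*Combined protocol and SAP*

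**What the plan says.** Section 2.3.2 singles out pancreatitis as a risk particularly of durvalumab with tremelimumab. Section 8.5 lists it among the immune-mediated events and refers their dose management to Table 7. Section 10.2 gives it its own bullet.

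Table 7 has no pancreatitis row, and none of 8.5.2 to 8.5.13 is about pancreatitis. The pancreatic content that does exist is:

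- The heading of the endocrinopathy row in Table 7: "exocrine event of amylase/lipase increased also included in this section". At Grade 2 and at Grade 3-4 that row says "Hold study therapy dose until patient is clinically stable". Where steroids were used, the Grade 3-4 entry says "after completion of the steroid taper, resume study therapy". It stops therapy only if the taper runs beyond 28 days.
- Section 8.5.8, which advises against steroids for modest enzyme rises without symptoms, and asks for an autoimmune antibody sample when an event such as pancreatitis may be autoimmune. For endocrinopathies of Grade 2 and of Grade 3 or 4 it says: "Study therapy can be resumed once event stabilizes and after completion of steroid taper".

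The general rule for any event treated with systemic steroids is in 8.2.1. Therapy is held, and if the taper is finished within 28 days, "Study therapy may then be resumed after completion of the steroid taper on Day 1 of the next scheduled cycle". Section 8.3 adds: "Dosing of study therapy will be done in tandem".

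**The concern.** A site facing severe pancreatitis is sent to Table 7 and finds no row. The two rules it would most naturally fall back on, 8.2.1 and the endocrinopathy row, both permit resumption, and neither has a grade limit or calls for a lower dose level. The endocrinopathy row is built around hormone deficits that can be replaced: its instructions concern endocrine work-up, an endocrinologist's guidance and hormone replacement. Nothing in the documents extends that reasoning to pancreatitis.

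What is at stake is patient safety and consistency between sites. In Cycles 1 to 4 redosing would be with both drugs. Two sites could treat the same Grade 4 event differently and both be within the protocol. The primary endpoint and the decision rule are not affected.

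**Working it through.** There is no planned figure to reproduce. The check is a count and a trace of one case through the rules.

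**Step 1. Match the 12 AESI bullets in 10.2 to Table 7 and 8.5.**

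| AESI bullet | Table 7 row | Subsection |
|---|---|---|
| Diarrhea/colitis | Diarrhea/enterocolitis | 8.5.4 |
| Pneumonitis/ILD | Pneumonitis | 8.5.3 |
| Hepatitis | Hepatitis; hepatitis by laboratory values | 8.5.5 |
| Neuromuscular toxicity | Peripheral neuromotor syndrome | 8.5.10 |
| Endocrinopathy | Endocrinopathy | 8.5.8 |
| Dermatitis/rash | Rash; bullous rash | 8.5.7 |
| Nephritis | Creatinine increased | 8.5.6 |
| Pancreatitis | none | none |
| Infusion reaction | Allergic/infusion reaction | 8.5.2 |
| Hypersensitivity | Allergic/infusion reaction | 8.5.2 |
| Myocarditis | Myocarditis | 8.5.12 |
| Myositis | Myositis | 8.5.13 |

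Matched: 11. Unmatched: 12 − 11 = 1, pancreatitis.

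**Step 2. Count the Grade 4 action by row.** Table 7 has 15 event rows: myocarditis, endocrinopathy, diarrhea, hepatitis, allergic/infusion reaction, hepatitis by laboratory values, creatinine, platelets, myositis, neurotoxicity, peripheral neuromotor syndrome, pneumonitis, rash, bullous rash, and non-immune events. All discontinue at Grade 4 except endocrinopathy: 15 − 1 = 14.

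**Step 3. Count the outright stops at Grade 3.** Myocarditis, hepatitis, allergic/infusion reaction, creatinine, pneumonitis and bullous rash: 6 of 15. The other 15 − 6 = 9 do not stop outright at Grade 3.

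**Step 4. Trace a Grade 4 pancreatitis with no clear alternative cause.**

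1. Section 8.5 treats it as potentially immune related.
2. Section 8.5.1 recommends prompt systemic steroids at Grade 3 or higher.
3. Under 8.2.1, steroids make a hold mandatory.
4. The event settles and the taper is completed within 28 days. Section 8.2.1 then allows resumption on Day 1 of the next scheduled cycle. The endocrinopathy row, if the site uses it, leads to the same place.
5. Neither route names a lower dose level. If the event fell in Cycles 1 to 4, both drugs would resume.

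**Step 5. See what else could stop therapy, and on what trigger.**

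| Safeguard | Trigger |
|---|---|
| 8.2.2: "An adverse event occurs that, in the opinion of the investigator or sponsor, contradicts further dosing" | Judgement |
| 12.4, investigator's decision to stop | Judgement |
| 8.2.1, taper over 28 days | Duration |
| 8.2.2, hold over 28 days for other reasons | Duration |
| 8.5.1, relapse on taper, leading to a taper over 28 days | Clinical course, then duration |
| 10.4.2 and 10.7.2, report within 24 hours | AESI of Grade 2 or higher; informs, sets no dose rule |
| 14.3, weekly call and monthly review | Calendar; inform, set no dose rule |

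None of these stops therapy because the event is Grade 4.

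**The case against.** The strongest reply is that redosing would be hard to reach in practice. Steroids force a hold, so nobody is dosed through the event. The event must be reported within 24 hours. Investigators with a patient on therapy are required to join a weekly call with the protocol officer (14.3). Under 8.2.2 therapy must stop if either the investigator or the sponsor thinks further dosing is contraindicated. Redosing therefore needs a Grade 4 event that settles, a taper finished in time, and no objection from either party. All of this stands, and it limits the likely harm. But the same oversight applies to myocarditis, nephritis and pneumonitis, and for those the protocol still writes a stop at Grades 3 and 4.

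A second reply is that Table 7 was never exhaustive. At least four rarer AESIs named in 10.2 (pericarditis, sarcoidosis, uveitis, vasculitis) also have no row. That is true. Pancreatitis differs in being bulleted and in being tied by 2.3.2 to this combination.

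Third, the last row of Table 7 stops therapy at Grade 4. It covers "AEs of non-immune mediated reaction requiring dose modification per investigator". A reader might infer that no Grade 4 pancreatitis of any kind has a written stop. The documents do not support that: a case with a clear non-immune cause can fall in this row. The row also cites 8.5.1, so a site might use it as a default, but its title confines it to non-immune events. For the immune-mediated case the contrast remains: a Grade 4 non-immune event in this row must stop, while a Grade 4 immune-mediated pancreatitis may be redosed.

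A reader might also infer that Grade 3 pancreatitis ought to be a mandatory stop. With 9 of 15 rows not stopping outright at Grade 3, the documents do not settle that.

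**Conclusion.** The gap is real and narrow. One of 12 bulleted AESIs has no dosing rule of its own, and the rules a site would reach permit, but do not require, resumption without dose reduction after a Grade 4 immune-mediated pancreatitis that settles with a taper of 28 days or less. That departs from 14 of 15 rows in the same table.

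The conclusion assumes that the event is immune-mediated or has no clear other cause, that the taper is completed within 28 days, and that neither investigator nor sponsor objects. It should not be read as saying that redosing is mandated or that oversight is absent. Nor does the lack of an enzyme threshold for releasing symptom-free patients count as a fault: elevated lipase was among the most frequent events in the phase 1 NSCLC study described in 2.5, and a strict threshold could end therapy needlessly.

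No pancreatitis rate for this regimen is given, so the expected number of affected patients among the 12 to 21 evaluable cannot be stated. The change is worth making because it closes a safety ambiguity at almost no cost.

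**What to change.** 1. Add a Table 7 row for clinical immune-mediated pancreatitis. Grade 4: discontinue. Grade 2-3: hold, resume only at Grade 1 or less after the taper, and discontinue if the taper exceeds 28 days. Leave any outright Grade 3 stop or dose reduction to the sponsor.
2. State in the endocrinopathy row and in 8.5.8 that raised amylase or lipase with signs or symptoms of pancreatic inflammation goes to the new row, and that the clinical pancreatitis grade governs, not the enzyme grade. Otherwise a high lipase with nonspecific abdominal pain could end therapy.
3. Optionally add a default row for immune-mediated events not otherwise listed, with discontinuation at Grade 4. Keep the 8.5.1 exception for inflammation attributed to local tumor response. This would also cover the rarer AESIs without rows.

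The cost is drafting. Table 2 already requires lipase and amylase before each cycle. The downside is small: a patient who recovers from Grade 4 pancreatitis loses the option of redosing and, if stopped before completing Cycle 2, is non-evaluable and is replaced under 14.2.

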 - For all patients with abnormal endocrine work up, except those with isolated hypothyroidism or Type 1 DM, and as guided by an endocrinologist, promptly initiate empiric IV methylprednisolone 1 to 2 mg/kg/day or equivalent, as well as relevant hormone replacement (e.g., hydrocortisone, sex hormones).
 - For adrenal crisis, severe dehydration, hypotension, or shock: immediately initiate intravenous corticosteroids with mineralocorticoid activity.
 - Isolated hypothyroidism may be treated with replacement therapy, without study therapy interruption, and without corticosteroids.
 - Isolated Type 1 diabetes mellitus may be treated with appropriate diabetic therapy, without study therapy interruption, and without corticosteroids.
 - Once improving, gradually taper immunosuppressive steroids (28 days of taper) and consider prophylactic antibiotics, antifungals and anti PJP treatment (refer to current NCCN guidelines for treatment of cancer-related infections [Category 2B recommendation]).
 - Report event to DSSM.

8.5.9 **Neurotoxicity**

Neurotoxicity (to include but not limited to limbic encephalitis autonomic neuropathy, excluding Myasthenia Gravis and Guillain-Barre)

- *Any Grade:*
 - Patients should be evaluated to rule out any alternative etiology (e.g., disease progression, infections, metabolic syndromes and medications, etc.).
 - Monitor patient for general symptoms (headache, nausea, vertigo, behavior change, or weakness).
 - Consider appropriate diagnostic testing (e.g. electromyogram and nerve conduction investigations) inclusive of neurology consult as indicated.
 - Perform symptomatic treatment with neurological consult as appropriate.
 - For study treatment dose management related to imAEs, see [Section 8.5.1](#) and [Table 7](#).
- *Grade 2:*
 - Report event to DSSM.
 - Obtain Neurology consult.
 - Sensory neuropathy/neuropathic pain may be managed by appropriate medications (e.g., gabapentin, duloxetine, etc.)
 - Promptly start systemic steroids prednisone 1-2mg/kg/day PO or IV equivalent.
 - If no improvement within 3-5 days despite prednisone 1-2mg/kg/day PO or IV equivalent consider additional workup and promptly treat with additional immunosuppressive therapy (e.g. IVIG).
- *Grade 3:*

Hold study therapy dose until resolution to Grade ≤ 1 . Permanently discontinue study therapy if Grade 3 imAE does not resolve to Grade ≤ 1 within 28 days.

 - Report event to DSSM.
 - Obtain Neurology consultation.
 - Consider hospitalization.

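### Both Table 7 endocrinopathy cells attach the hypothyroidism/Type 1 diabetes exception only to the steroid sentence, leaving an unqualified hold that Section 8.5.8 does not apply to these patients

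*Combined protocol and SAP*

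**What the plan says.** **Protocol 8.4, Table 7, Endocrine disorders.** The row label reads "Endocrinopathy (e.g., hyperthyroidism, hypothyroidism, Type 1 diabetes mellitus, hypophysitis, hypopituitarism, and adrenal insufficiency", so both conditions at issue fall within it. The Grade 2 and Grade 3-4 cells are built the same way. The first sentence concerns short-term corticosteroids and hormone replacement and contains the clause "except those with isolated hypothyroidism or Type 1 DM". A separate sentence follows: "Hold study therapy dose until patient is clinically stable". The bullets after it deal with steroid tapers and long-term steroid replacement.

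**Protocol 8.5.8.** Here the exception is on the hold itself. At Grade 2: "For Grade 2 endocrinopathy other than hypothyroidism and Type 1 diabetes mellitus, hold study therapy dose until patient is clinically stable". At Grade 3-4: "For Grade 3 or 4 endocrinopathy other than hypothyroidism and Type 1 diabetes mellitus, hold study therapy dose until endocrinopathy symptom(s) are controlled". The bullets add that isolated hypothyroidism at Grade 2 "may be treated with replacement therapy without treatment interruption and without corticosteroids" and that Grade 2 patients with Type 1 diabetes "may be treated with appropriate diabetic therapy, without study therapy interruption, and without corticosteroids". At Grade 3-4, "Isolated hypothyroidism may be treated with replacement therapy, without study therapy interruption, and without corticosteroids", and isolated Type 1 diabetes is treated in the same way.

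**Cross-references.** Section 8.3 places the toxicity instructions in Table 7. Section 8.4 and the table row send the reader to 8.5. Section 8.5 describes its guidelines as recommended and, like 8.5.8, sends the reader back to Table 7 for dose management.

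**The concern.** Table 7 is the operative dosing table. A site that applies it sentence by sentence would hold both drugs for a patient with Grade 2-4 isolated hypothyroidism or Type 1 diabetes. A site that works from 8.5.8 could continue treatment. Similar patients could therefore be managed differently, and some doses could be delayed or omitted without need. Tremelimumab is the more exposed drug because only four doses are planned.

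**Working it through.** The protocol states no figure on this point to reproduce. The check compares the texts and then bounds what a hold could cost.

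**Step 1: the texts side by side**

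| Text | Is the exception on the hold? | Use of *isolated* | Hold ends when |
|---|---|---|---|
| Table 7, Grade 2 | No; on the steroid sentence only | Once, before hypothyroidism | Patient clinically stable |
| Table 7, Grade 3-4 | No; on the steroid sentence only | Once, before hypothyroidism | Patient clinically stable |
| 8.5.8 Grade 2 hold | Yes | Not used | Patient clinically stable |
| 8.5.8 Grade 2 bullets | No interruption needed | Hypothyroidism yes, Type 1 diabetes no | n/a |
| 8.5.8 Grade 3-4 hold | Yes | Not used | Symptoms controlled |
| 8.5.8 Grade 3-4 bullets | No interruption needed | Both | n/a |

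On the literal reading, Table 7 and 8.5.8 differ at Grade 2 and at Grade 3-4. The Grade 3-4 end-point of the hold differs as well.

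**Step 2: does the whole-cell reading cure it?** Suppose the exception governs everything in the cell. The conflict then goes, but Table 7 has no dosing action at Grades 2-4 for two conditions named in its own row. Two features also count against that reading:
- Section 8.5.8 Grade 2 has nearly the same steroid sentence with the same exception, and still puts a separate exception on the hold.
- The Grade 2 immune-mediated hepatitis cell of Table 7 expressly exempts certain patients with liver metastases before it states the hold. When the table exempts patients from a hold there, it says so.

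**Step 3: when would a dose be late or lost?** Inputs: dosing may move 3 days either side of the scheduled date (8.2); a cycle is 28 days; pre-dose tests are done within 72 hours before Day 1 (Table 2).
- Event found 0 to 3 days before Day 1: 0 + 3 = 3 days to 3 + 3 = 6 days until the window closes.
- Event found on Day 2 of a cycle: 27 days to the next Day 1, and 27 + 3 = 30 days until the window closes.

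A patient who is stable within that time loses no dose, even on the literal reading.

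**Step 4: size if one dose is omitted.** Planned doses are 4 of tremelimumab and 24 of durvalumab (Section 1.0 and Table 4).
- Cycles 2-4: 1/4 = 25% of tremelimumab doses and 1/24 = 4.2% of durvalumab doses.
- Cycles 5-24: 1/24 = 4.2% of durvalumab doses.
- One omitted dose with restart on the next scheduled Day 1 is a 28-day delay. The discontinuation rule in 8.2.2 applies to more than 28 days, so it is not triggered.

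**Step 5: how many patients?** The documents give neither a rate of these events in this population nor an expected length of hold, so no number is estimated.

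**The case against.** The strongest reply is that this is an ambiguity and not a conflict. Each cell opens by setting these patients apart, the bullets after the hold concern steroid-treated patients, and the row points to 8.5.8, where the exemption is explicit. That reading is reasonable and cannot be excluded. It does not fully answer the point, because the table is then silent on two listed conditions, and 8.5.8 itself refers dose management back to Table 7.

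A second reply stands in full: 8.5.8 only permits continuation. A reader might infer that it requires these patients to continue, so that a site holding under Table 7 breaches the protocol. The wording does not support that; the mismatch is between an instruction and a permission.

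A third reply also stands: the uneven use of *isolated* matters only in edge cases. A patient with hypothyroidism and Grade 2 hypophysitis is held under 8.5.8 with or without the word. The word bears on cases such as hypothyroidism together with Type 1 diabetes, or a second endocrinopathy of Grade 1.

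Finally, divergence is likely to be noticed. Endocrinopathies of Grade 2 or higher are reported to the sponsor's study management department within 24 hours (10.4.2, 10.7.2). Investigators with a patient on therapy must join a weekly call, and a medical review team meets monthly (14.3). These safeguards may reveal the difference, but they do not say which text to follow.

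**Conclusion.** The point holds and is minor. The exception is misplaced for a table that is meant to direct dosing, and nothing in the protocol says which text prevails. The consequence is limited to possible unnecessary or inconsistent holds. The loss figures of 25% and 4.2% are conditional: the site must follow the literal wording, the patient must still be unstable when the dosing window closes, and the dose must be omitted rather than given.

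A reader might go further and infer that lost doses would make patients non-evaluable or weaken the Simon two-stage decision rule. The documents do not support that. They give no event rate and no length of hold, one omitted dose does not force discontinuation under 8.2.2, and non-evaluable patients are replaced.

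**What to change.** 1. **Table 7, Grade 2 cell.** Limit the hold sentence to endocrinopathy other than *isolated* hypothyroidism or *isolated* Type 1 diabetes mellitus, then keep the existing instruction, "Hold study therapy dose until patient is clinically stable". Add a sentence stating that the isolated forms of either condition may be managed with replacement or diabetic therapy while study therapy continues.
2. **Table 7, Grade 3-4 cell.** Use the same text. Choose one end-point for the hold, either clinical stability or symptom control, and use it in both Table 7 and 8.5.8.
3. **Section 8.5.8.** Add *isolated* to the Grade 2 and Grade 3-4 hold sentences and to the Grade 2 Type 1 diabetes bullet, so that the scope of the exemption is the same throughout.

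If the sponsor does intend these patients to be held as a precaution, 8.5.8 is the text to change. The cost is a reworded hold and one added sentence in two table cells, one word in three places in 8.5.8, and one aligned end-point. No procedure, visit or data item changes.
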